7.3.4.2 Central Read

Additionally a central radiology read of scans will be performed by SYNARC/BioClinica. The revised IWG criteria definitions [4] will also be applied. Details of the central read are described in the Independent Review Charter, Version 1.0, 01-JUL-2013, provided by SYNARC.

The independent reviewers (two primary radiologists) will be presented with all time points sequentially in chronological order, and will provide assessments for each time point. For the

overall tumor assessment of the central read a slightly different terminology is used:

- CR - Complete response
- PR - Partial response
- SD - Stable disease
- PD - Relapsed or progressive disease
- NE - Non-Evaluable (can be applied if repeated measurements cannot be applied for reasons such as inadequate or missing imaging and when progression/relapse cannot be assigned for the visit overall response)
- ND - No Disease (this category is used if there is no tumor and there was no tumor at baseline)

Once the independent reviews for all time points in the course of the study have taken place, all time points for a particular patient will be again reviewed together by the two independent reviewers in a global patient review over all time points. In their global patient review the two independent reviewers will determine:

- best overall response (defined as best response the subject had since treatment started taking into account scheduled and unscheduled visits)
- date of the best overall response
- duration of best overall response (calculated by the system as time from first response to progression if patient is PD at a specific visit)
- date when progression/relapse occurred

Finally, an adjudicator radiologist will perform adjudication, in case there is any discrepancy in the global patient review of the two primary radiologists. The adjudicator will review both initial readings and will record a new review that will agree with either of the duplicate reviews. Thus, the adjudicator will need to agree to the complete reading of one of the primary radiologists (all assessments by visit and all variables from corresponding global review). A mandatory comment will need to be recorded. The adjudicated reading results will be considered as the results for the involved patients.

There may be rare cases where the two primary radiologists disagree in some of the overall assessments by visit, but agree in the global patient review. In these cases no adjudication will be performed. Thus for the overall assessment by time point, descriptive tables will be based on

the following results:

- Assessment of the reader the adjudicator agrees with, in case adjudication was performed
- Worst response assessment of the two primary radiologists at each visit in case no adjudication was performed

All other variables described below are only based on the variables from global review which are adjudicated in case of discrepancies between the two primary radiologists. The term “central reviewer” used below refers to the adjudicator in case adjudication is performed or to the primary radiologists (in case global patient review of the two primary radiologists are identical and no adjudication is necessary).

In case any anti-tumor treatments other than MOR00208 are given before end of study (see also section 8.3), it is regarded as protocol non-compliance. Following a conservative approach for statistical analysis, the following steps will be implemented by [REDACTED] biostatistics: tumor assessments of the two primary radiologists after start of other anti-tumor treatment which are non-PD will not be taken into account, whereas assessments of PD will still be taken into account. Moreover, if the date of best overall response as provided by the adjudicator is after start of anti-tumor treatment, the date will be set to missing and the best overall response to “not evaluable”. This ensures that a progress is still included in the analysis if an anti-tumor treatment has been started based on clinical progression, but the image confirming PD was done at a later time point. A response after start of anti-tumor treatment will, however, not be counted for best overall response.

Tumor Response categories (Central Read) will be evaluated in terms of absolute and percentage frequencies by visit

Best overall response (Central Read) will be directly provided by the central reviewer (SYNARC uses the terminology best overall response or best response).

Overall response rate (ORR) (Central Read) will be evaluated as the rate of patients who have a best overall response of PR or CR.

Overall rate of SD (disease control rate) (Central Read) will be evaluated as the rate of patients who have a best overall response of PR, CR or SD.

Duration of best overall response (Central Read): Duration of best overall response will be defined as the time from date of best overall response (as provided by the central reviewer) until first date that recurrent or progressive disease is objectively documented. The duration of

Statistical Analysis Plan Final Version 4.0

best overall response will be calculated in the subgroup of all patients showing any response; confirmation of response will not be required. Patients who showed a response but did not show PD or recurrence until end of study or before withdrawal (according to the central reviewer) are considered censored at the timepoint of last response assessment. Deaths without documented progression before death (according to the central reviewer) are also considered as censored at date of last response assessment.

Time to response (Central Read): Time to response will be defined as the time from Cycle 1, Day 1 (first administration of study drug) until the date of best overall response (as provided by the central reviewer) if best overall response is PR or CR. Patients who do not have a response to treatment will be censored at the date of their last tumor assessment.

Time to progression (Central Read): Time to progression is defined as the time from Cycle 1, Day 1 (first administration of study drug) until date of progression/relapse (as provided by the central reviewer). Patients who do not show any documented progression (according to the central reviewer) before the end of study or before withdrawal or before death are considered censored using the last date with a tumor assessment as censoring date (irrespective of when the patient died).

Progression-free survival (Central Read): Progression-free survival is defined as the time from Cycle 1, Day 1 (first administration of study drug) until date of progression/relapse (as provided by the central reviewer) or date of death from any cause (as given in the eCRF). If the patient does not show any documented progression before death (according to the central reviewer), the date of progression/death will be the date of death if death occurs within 2 months after the last date with a tumor assessment. If death occurs after 2 months after the last date with a tumor assessment or the patient did not progress or die until end of study or before withdrawal, the patient will be analyzed as censored using the last date with a tumor assessment as censoring date.

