7.3.4 Efficacy

7.3.4.1 Investigator Assessment

The Investigator will assess tumor response at specific study visits according to the criteria for NHL as defined in Section 17.4 of the study protocol. All of the criteria are based on the revised IWG response criteria [4].

The categories of overall tumor response assessment of the Investigator are as follows:

- CR - Complete remission
- PR - Partial remission
- SD - Stable disease

- PD - Progressive disease
- Missing (if response assessment is not done)

In case of progressive disease, the date of progression is given by the Investigator. In case any anti-tumor treatments other than MOR00208 are given before end of study (see also section 8.3), it is regarded as protocol non-compliance. Following a conservative approach, tumor assessments of the Investigator after start of other anti-tumor treatment which are non-PD will not be taken into account for any of the derived efficacy variables described below, whereas assessments of PD will still be taken into account. This ensures that a progression is still included in the analysis if an anti-tumor treatment has been started based on clinical progression, but the image confirming PD was done at a later time point. A response assessment provided by investigator after start of other than protocol indicated anti-tumor treatment will, however, not be counted for overall best response.

Tumor Response categories (Investigator) will be evaluated in terms of absolute and percentage frequencies by visit.

Overall best response (Investigator) will be defined as best response across the following time points: end of the second, end of third cycle, during a response assessment in the follow-up period or at an unscheduled assessment after end of second cycle.

Overall response rate (ORR) (Investigator) will be evaluated as the rate of patients who met the criteria of PR or CR at the end of either the second or third cycle or during a response assessment in the follow-up period (i.e. who have an overall best response of PR or CR).

Overall rate of SD (disease control rate) (Investigator) will be evaluated as the rate of patients who met the criteria of PR, CR or SD at the end of either the second or third cycle or during a response assessment in the follow-up period (i.e. who have an overall best response of PR, CR or SD).

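### The central-read rule for new anti-tumour treatment can discard a response documented before that treatment began (SAP 7.3.4.2)

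*SAP*

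**What the plan says.** SAP 7.3.4.2 defines central BOR in the global patient review as the "best response the subject had since treatment started taking into account scheduled and unscheduled visits". It is one value per patient, with no stop at the start of another anti-tumour treatment. For the analysis, BOR "will be directly provided by the central reviewer", and "All other variables described below are only based on the variables from global review which are adjudicated in case of discrepancies". Central ORR "will be evaluated as the rate of patients who have a best overall response of PR or CR".

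The same section has two steps for patients who receive another anti-tumour treatment:

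- At visit level, assessments after the new treatment "which are non-PD will not be taken into account, whereas assessments of PD will still be taken into account".
- At global level, "if the date of best overall response as provided by the adjudicator is after start of anti-tumor treatment", then "the date will be set to missing and the best overall response to" not evaluable.

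The stated purpose is that a response arising after the new treatment should not count towards BOR.

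For the investigator read, SAP 7.3.4.1 drops non-PD assessments after the new treatment from all derived efficacy variables, and adds: "A response assessment provided by investigator after start of other than protocol indicated anti-tumor treatment will, however, not be counted for overall best response". There is no reset to not evaluable.

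**The concern.** The global-level step removes more than the late response. It replaces the patient's whole BOR with not evaluable, even if a valid response was read before the new treatment. The visit-level step cannot repair this, because central BOR and ORR are taken from the global review and not rebuilt from visits.

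The consequences for such a patient are:

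- The patient stays in the ITT denominator of central ORR (SAP 2.2.2, secondary endpoint 10) but leaves the numerator.
- Central duration of best overall response starts at a date that is now missing, and time to response treats the patient as a censored non-responder.
- The by-visit central table can show a PR for a patient whose BOR is not evaluable.
- SAP 9.1 compares central with investigator best response and divides central responders by investigator responders. Part of any disagreement would then come from the analysis rule and not from the readers.

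The trigger also refers only to a date given by the adjudicator. Many patients may have no adjudication, and the section itself defines the central reviewer to cover both situations.

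**Working it through.** **The plan's own figure.** SAP 5 plans 30 patients per subtype, a true ORR of 30%, 9 responses and a lower 95% limit of 14.7%. SAP 9.1 specifies Clopper-Pearson intervals. The lower limit is the 2.5% quantile of Beta(9, 22) = 14.73%, which agrees. The upper limit is the 97.5% quantile of Beta(10, 21) = 49.4%. The documents give no figure for the effect of the new-treatment rule.

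**Applying the rule to response sequences.** The central column uses the reset as if it applied to every patient. The comparison column drops non-PD assessments after new treatment, as in SAP 7.3.4.1. I assume that BOR is dated at the first occurrence of its category; the SAP does not say so.

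| Before → after new treatment | Global BOR | Central result | Pre-treatment best | Effect |
|---|---|---|---|---|
| PR → CR | CR | NE | PR | responder lost |
| PR, PD → CR | CR | NE | PR | responder lost |
| PR → PR | PR | PR | PR | none |
| CR → CR | CR | CR | CR | none |
| PR → SD or PD | PR | PR | PR | none |
| SD → PR or CR | PR or CR | NE | SD | ORR same; disease control loses one |
| PD → PR | PR | NE | PD | ORR same |

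A responder is lost only when a PR before the new treatment is followed by a later-dated CR after it.

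**Size per affected patient.** The change in central ORR is −1/N.

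- N = 30, one patient: 9/30 = 30.0% (14.7 to 49.4) becomes 8/30 = 26.7% (12.3 to 45.9), a fall of 3.3 points.
- N = 30, two patients: 7/30 = 23.3% (9.9 to 42.3), a fall of 6.7 points.
- N = 10, one patient: 3/10 = 30.0% (6.7 to 65.2) becomes 2/10 = 20.0% (2.5 to 55.6), a fall of 10 points.
- N = 120, one patient: 36/120 = 30.0% becomes 35/120 = 29.2%, a fall of 0.8 points.

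The number of affected patients is not in the documents. Zero to two per cohort is my assumption; with zero, nothing changes.

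**The adjudicator wording, read literally.** The reset then applies only where adjudication took place. A non-adjudicated patient with SD before and PR after the new treatment keeps a BOR of PR and counts as a responder, against the paragraph's aim. This error raises central ORR by 1/N.

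**The case against.** The strongest reply is that the triggering case should hardly arise. Protocol 9.8 bars other NHL-specific therapy and asks for contact with the medical monitor before any is started. Protocol 9.11.1 lists new cancer therapy as a reason for withdrawal, and SAP 8.3 says that it should lead to exclusion from further participation. Follow-up visits run only until relapse (Protocol 10.3), and the response assessment at the end-of-study visit is physical examination only (Protocol 10.5). An affected patient must respond, take a prohibited drug, stay in the study, be scanned again and improve to CR. The rule is also described as conservative, and the protocol plans no inferential testing (14.10).

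The point about rarity stands and limits the weight of the finding. It does not make the rule right. The SAP foresees assessments after new treatment, since both 7.3.4.1 and 7.3.4.2 legislate for them. Conservatism explains ignoring the late CR; it does not explain discarding the earlier PR.

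Three stronger readings are tempting, and the documents do not support them:

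- A reader might infer that an earlier response is lost whenever the BOR date follows new treatment. With SD or PD before, there is no response to lose, and not counting the later one is the intended handling.
- A reader might infer that central ORR is biased low by a known amount. The 1/N figures are per-patient arithmetic, not an estimate, and the literal adjudicator wording works in the opposite direction.
- A reader might infer that the concordance rate must fall. SAP 9.1 excludes patients assessed by the investigator but not by central review, and does not say whether a patient reset to not evaluable belongs there. The ratio of central to investigator responders would fall in any case.

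On the adjudicator wording, the intent is clear from the paragraph's closing sentence and the definition of central reviewer, so this is a drafting gap.

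**Conclusion.** The point holds in a limited form. The reset has no fallback, goes further than its own stated aim and is not parallel to the investigator rule. It turns a central PR-then-CR patient into a non-responder, and takes an SD-then-response patient out of the central disease control rate. The ORR cost is 1/N per PR-then-CR patient. The number affected is unknown, probably small and possibly zero. Only the central-read results and their comparison with the investigator read are touched; the primary ORR is by investigator and does not change.

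The conclusion rests on BOR being dated at first occurrence. If a later date were recorded, the reset could also catch patients who held the same response before and after the new treatment. The Independent Review Charter might settle the dating, but it is not among the documents.

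**What to change.** Amend SAP 7.3.4.2 as follows:

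1. Where the BOR date is after the start of other anti-tumour treatment, derive central BOR and its date from visit-level central reads dated before that start.
2. Use the reads of the reader with whom the adjudicator agreed. If there was no adjudication, use the worse of the two readers at each visit, as the section already does for the by-visit tables. This also covers patients whose readers agree globally but differ at some visits.
3. Set BOR to not evaluable only if no evaluable read exists before the new treatment.
4. Replace the reference to the adjudicator with the central reviewer, so that the rule covers all patients.
5. State that BOR is dated at the first occurrence of its category, and report how many patients the rule affects.

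The cost is a short SAP change and some programming. The independent reviewers already provide assessments at each time point, so no new reading is needed, and the rule can be fixed without looking at results. The downside is that for these few patients BOR comes from visit-level reads and not from the global review, and taking the worse of two readers is slightly conservative.

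### Central-read duration of response starts, and central-read time to response ends, at best response instead of first CR or PR, and the SAP conflicts with itself on the duration start

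*SAP*

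**What the plan says.** **Protocol.** Sections 10.6 and 14.5.1 both run duration of response from the first time CR or PR criteria are met to first documented relapse or progression. Neither names a reader. Time to response is not a protocol endpoint.

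**SAP, investigator read (7.3.4.1).** Duration starts at first CR or PR, and time to response ends there.

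**SAP, central read (7.3.4.2).**
- Among the outputs of the global patient review: "duration of best overall response (calculated by the system as time from first response to progression if patient is PD at a specific visit".
- As the derived analysis variable: "Duration of best overall response will be defined as the time from date of best overall response (as provided by the central reviewer".
- Central time to response runs "until the date of best overall response (as provided by the central reviewer) if best overall response is PR or CR".
- On the source of the derived variables: "All other variables described below are only based on the variables from global review". The listed global outputs include the date of best overall response but no date of first response.

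**SAP, reporting.** Section 9.2 requires every secondary efficacy analysis on both reads, with Kaplan-Meier event percentages for duration at 2, 4, 6 and 12 months. It names the central variable duration of best overall response and the investigator variable duration of response, but uses one name, time to response, for both reads. Section 12 lists the added central-read response rate and two other changes. It does not mention a different start for central duration.

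**The concern.** Duration of response is a protocol secondary objective and endpoint. Reporting it on two reads is informative if differences between the tables reflect the assessors. Under the derived definition in SAP 7.3.4.2, a patient who goes from PR to CR gets a shorter central duration and a longer central time to response than on the investigator read, even when both assessors read every scan identically.

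There is also a programming ambiguity. Two statements in the same SAP section give a variable of the same name different starts, so two programmers could each follow the text and produce different central tables. If the best-response start is used, no central analysis of duration as the protocol defines it is clearly specified, and section 12 does not tell the reader so.

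**Working it through.** The plan gives no figure that depends on this point, so there is none to reproduce. The check is a comparison of text, followed by the size of the shift on the nominal visit schedule.

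**1. Definitions side by side**

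| Place | Duration starts at | Time to response ends at |
|---|---|---|
| Protocol 10.6, 14.5.1 | first CR or PR | not defined |
| SAP 7.3.4.1, investigator | first CR or PR | first CR or PR |
| SAP 7.3.4.2, global-review output | first response | not listed |
| SAP 7.3.4.2, derived central variable | best overall response | best overall response |

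The rows agree for a patient whose first response is also the best response. They differ only when PR deepens to CR.

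**2. Nominal days**, with Cycle 1 Day 1 as day 1 (protocol 10.2 and 10.3; month = 30.4375 days, SAP 7.1)

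- Cycle 2 Day 28: 28 + 28 = 56. Cycle 2 Day 22: 28 + 22 = 50.
- Cycle 3 Day 1: 50 + 14 = 64. Cycle 3 Day 28: 64 + 27 = 91.
- Follow-up visit (FU) 1: 91 + 28 = 119. FU2: 119 + 42 = 161. FU3: 161 + 42 = 203 (no response assessment).
- FU4: 203 + 3 × 30.4375 = 294.3. FU5: 385.6. FU6: 476.9.

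**3. Shift per patient**, first PR at Cycle 2 Day 28: (day of CR − 56) / 30.4375

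| CR first read at | Days | Months |
|---|---|---|
| Cycle 3 Day 28 | 91 − 56 = 35 | 1.15 |
| FU2 | 161 − 56 = 105 | 3.45 |
| FU4 | 294.3 − 56 = 238.3 | 7.83 |
| FU5 | 385.6 − 56 = 329.6 | 10.83 |

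Central duration is shorter, and central time to response longer, by this amount. Their sum, used in the SAP 9.2 time-on-study listing, does not change.

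**4. Against the landmarks**, both assessors reading identically

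- PR at Cycle 2 Day 28, CR at FU2, progression at FU4: (294.3 − 56)/30.4375 = 7.83 months from first response; (294.3 − 161)/30.4375 = 4.38 from best response. This crosses 6 months.
- The same with progression at FU6: (476.9 − 56)/30.4375 = 13.83 against (476.9 − 161)/30.4375 = 10.38. This crosses 12 months.
- CR at Cycle 3 Day 28, progression at FU4: 7.83 against (294.3 − 91)/30.4375 = 6.68. No landmark is crossed.

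**5. Weight of one patient who crosses a landmark**, nobody censored earlier

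- One full subtype cohort at the plan's assumed rate (SAP section 5): 0.30 × 30 = 9 responders; 1/9 = 11.1 points.
- All responders pooled, assuming four full cohorts: 4 × 9 = 36; 1/36 = 2.8 points.

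SAP 9.2 says duration and time to response are presented for all responders overall, while its general rule is presentation by subtype unless specified otherwise. Either denominator is therefore possible.

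**6. Can a first-response date be derived from what is held?** Both central readers assess every time point. The SAP supplies "an adjudicator radiologist will perform adjudication, in case there is any discrepancy in the global patient review", and for by-visit tables otherwise uses "Worst response assessment of the two primary radiologists at each visit in case no adjudication was performed". Readers who were not adjudicated agree on best response and its date. The SAP does not say, however, that the global review must match the by-visit reads, and it allows by-visit disagreement alongside global agreement. The worst-of-two rule could therefore give a date later than best response, or none, so a fallback is needed.

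**The case against.** The best defence is that central duration is a supportive analysis and a deliberately different variable. The investigator read is primary, it follows the protocol start date, and the only central-read item in the SAP's endpoint list is the response rate. Section 9.2 gives central duration its own name. The global-review wording describes a vendor system whose details are in a charter not supplied, and first response there could mean the first date in the best category.

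Part of this stands. The different start may be intended, and it would be wrong to infer that the protocol's duration endpoint goes unreported. But the distinct name does not resolve the matter, because the SAP attaches that name to a first-response start as well, and the text does not say that first response means the first date in the best category. Nor does the defence cover time to response, which has one name and two end dates.

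Three stronger readings are tempting and not supported:
- **That the central read is made to flatter the drug.** The shift shortens duration and lengthens time to response.
- **That a common start date would leave reader disagreement as the only difference.** Investigator duration censors deaths from causes other than progression and asks for cause of death. Central duration censors every death without centrally documented progression. The central read is also a radiology read, while the protocol's response criteria include bone marrow and palpation.
- **That the 11.1-point figure is the expected effect.** It is one patient in one subtype. Pooled reporting gives 2.8, and the number of such patients is unknown.

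**Conclusion.** The point holds as a definitional inconsistency in a secondary analysis and should be corrected. Central duration starts, and central time to response ends, at best response. The protocol and investigator definitions of duration use first CR or PR, the SAP is inconsistent on the central start on a plain reading, and section 12 is silent. The time-to-response mismatch is within the SAP only, and that variable is not in its endpoint list.

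For a PR at Cycle 2 Day 28 that deepens, the shift is 1.15 to 10.83 months for CR between Cycle 3 Day 28 and follow-up visit 5. This rests on nominal visit dates; visit windows move it slightly. The documents give no PR-to-CR rate, so no effect on a median or cohort curve is claimed. With no deepening it is zero.

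The primary investigator response rate, investigator duration, and central response rate, time to progression and progression-free survival are unaffected. The study plans no inferential testing.

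The SAP cites protocol Amendment 4, while the protocol supplied is Amendment 5. The conflicts within the SAP do not depend on that.

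**What to change.** 1. In SAP 7.3.4.2, start central duration at, and end central time to response at, the first central-read CR or PR.
2. Restrict both to central responders as the central response rate defines them: best overall response PR or CR after the rule for other anti-tumour treatment. Under that rule, when best response falls after such treatment, "the date will be set to missing and the best overall response to" not evaluable. The present wording, "best overall response will be calculated in the subgroup of all patients showing any response", should be aligned with this set so that no patient enters without a start date.
3. Take the date from the by-visit reads already held: the adjudicator-selected reader where there was adjudication, otherwise the worst-of-two rule. If that gives a date later than best overall response, or none, use the date of best overall response.
4. Amend the sentence limiting these variables to global-review outputs, and reconcile the global-review description of duration with the derived definition.
5. Keep duration from best response as a labelled supplement, and record the change in section 12.
6. Align the handling of deaths between 7.3.4.1 and 7.3.4.2, or state the difference beside the tables.
7. Settle whether non-responders enter time to response: 7.3.4.1 and 7.3.4.2 censor them, while 9.2 presents responders.

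The cost is SAP wording and one derivation. No new reads are needed.
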